1.2 ABBV-CLS-7262 Therapeutic Rationale

ABBV-CLS-7262 drug product consists of film-coated granules, to be administered orally on a QD schedule. The doses selected for this study are based on the totality of available evidence: *in vitro* TDP-43 stress granule dissolution data and an optic nerve crush mouse model of ISR-dependent acute neuronal injury to predict efficacious doses in patients with ALS, PK data from Study M20-015 (healthy subjects) to support adequate CSF exposure at the selected doses, and PET data in NHPs to support adequate (>95%) target occupancy at the selected doses. The planned doses of 120 mg and 240 mg are anticipated to be safe and well-tolerated based on the totality of safety data from human clinical studies in healthy subjects and participants with ALS to date.

The study population will include participants with both sporadic and familial forms of ALS.

ABBV-CLS-7262 is an investigational product (IP), which based on *in vitro* and *in vivo* evidence is hypothesized to benefit patients with ALS via attenuation of a chronic ISR, restoration of protein synthesis, and dissolution of TDP-43-containing stress granules in nervous system tissue. In addition to the proposed therapeutic rationale for the sporadic form of ALS, it is hypothesized that the mechanism of action of ABBV-CLS-7262 suppresses Repeat Associated Non-AUG (RAN) translation in C9orf72 mutation carriers and resultant production of dipeptide repeats (DPRs), potentially affording a unique benefit to this patient population. The encouraging nonclinical results, along with the favorable safety and tolerability profile in human studies to date, support testing the therapeutic hypothesis that ABBV-CLS-7262 may slow disease progression in people with ALS.

2. OBJECTIVES

2.1 Study Objectives

Primary Efficacy Objective:

• To evaluate the efficacy of ABBV-CLS-7262 on ALS disease progression.

Secondary Efficacy Objective:

- To evaluate the effects of ABBV-CLS-7262 on selected secondary measures of ALS disease progression, including survival.
- To evaluate the effects of ABBV-CLS-7262 on serum neurofilament light chain (NfL) as a biomarker of ALS disease progression.

Safety Objectives:

• To evaluate the safety of ABBV-CLS-7262 in patients with ALS.

Pharmacokinetics Objective:

• To quantify the steady state concentrations of A-1684909 and/or any active or inactive metabolites in plasma after long-term oral dosing of ABBV-CLS-7262 QD.

Exploratory Objectives:

• To evaluate the effects of ABBV-CLS-7262 on selected biomarkers and exploratory endpoints.

2.2 Study Endpoints

RCT Database Lock: Last Participant Completes Week 24

Primary Efficacy Endpoint:

• Change from baseline to Week 24 in disease severity as measured by the ALS Functional Rating Scale-Revised (ALSFRS-R) total score and mortality.

Secondary Efficacy Endpoints:

- Change from baseline to Week 24 in function as assessed by ALSFRS-R total score.
- Change from baseline to Week 24 in respiratory function as assessed by slow vital capacity (SVC).
- Change from baseline to Week 24 in upper limb muscle strength as measured isometrically using hand-held dynamometry (HHD) and grip strength.
- Change from baseline to Week 24 in serum NfL.

• Change from baseline to Week 24 in activities of daily living (ADL) as assessed by the ALSAQ-40 ADL/independence domain score

Safety Endpoints:

- Treatment-emergent adverse and serious adverse events.
- Clinical laboratory tests, vital signs, and ECG parameters.
- Treatment-emergent suicidal ideation and suicidal behavior.

Pharmacokinetics Endpoint:

• Steady state concentrations of A-1684909 and/or any active or inactive metabolites of interest in plasma.

Exploratory Endpoints:

- Change from baseline to Week 24 in ALSFRS-R domain scores.
- Change from baseline to Week 24 in lower limb and combined upper and lower limb muscle strength (HHD).
- Changes from baseline to Week 24 in biofluid biomarkers of neurodegeneration, ALS disease, and the ISR pathway.
- Changes from baseline to Week 24 in patient-reported outcomes including the ALSAQ-40 total score and domain scores (physical mobility, eating and drinking, communication, and emotional reactions) and CNS-BFS.
- Change from baseline to Week 24 in ALS disease severity based on King's Staging.
- Change from baseline to Week 24 in ROADS.
- Changes from baseline to Week 24 in quantitative voice characteristics.
- Time to clinical events: first hospitalization due to a serious adverse event (SAE), first hospitalization due to an ALS-related SAE, first use of assisted ventilation, first placement of a feeding tube, first time reaching King's stage 4a or 4b, death or death equivalent, death alone.

ATE Database Lock: Last Participant Completes ATE Week 52 or Discontinues from the Study

Efficacy Endpoints:

- Combined Assessment of Function and Survival (CAFS) from baseline to ATE Week 52.
- Change from baseline to ATE Week 52 in function as assessed by ALSFRS-R total score.
- Change from baseline to ATE Week 52 in respiratory function as assessed by slow vital capacity (SVC).
- Overall survival defined as death or death equivalent through to the end of the ATE period (per section 3.3).

• Changes from baseline to ATE Week 52 in activities of daily living (ADL) as assessed by the ALSAQ-40 ADL/independence domain score.

Safety Endpoints:

- Treatment-emergent adverse and serious adverse events.
- Clinical laboratory tests, vital signs, and ECG parameters.
- Treatment-emergent suicidal ideation and suicidal behavior.

Exploratory Endpoints:

- Change from baseline to ATE Week 52 in function assessed by ALSFRS-R domain scores
- Change from baseline through to the end of the ATE Period (per section 3.3) in function (ALSFRS-R total score and domain scores).
- Change from baseline to ATE Week 52 in upper limb, lower limb, and combined upper and lower limb muscle strength (HHD) and grip strength.
- Changes from baseline to ATE Week 52 in biofluid biomarkers of neurodegeneration, ALS disease, and the ISR pathway.
- Changes from baseline to ATE Week 52 in patient-reported outcomes including the ALSAQ-40 total score and domain scores (physical mobility, eating and drinking, communication, and emotional reactions) and CNS-BFS.
- Change from baseline to ATE Week 52 in ALS disease severity based on King's Staging.
- Change from baseline to ATE Week 52 in ROADS.
- Changes from baseline to ATE Week 52 in quantitative voice characteristics.

2.3 Study Comparisons

- The primary comparison of interest is between the ABBV-CLS-7262 120 mg dose group and the shared concurrent placebo group when evaluating primary and secondary endpoints in the RCT data set.
- The primary comparison of interest in ATE is between ABBV-CLS-7262 120 mg RCT/ABBV-CLS-7262 120 mg ATE vs. placebo RCT/ABBV-CLS-7262 120 mg ATE based on combined RCT and ATE data sets.
- Comparisons involving the ABBV-CLS-7262 240 mg dose group and comparisons other than the primary comparison of interest are exploratory for both RCT and ATE data sets.
- Dose-dependent contrasts are of primary interest for pharmacokinetic endpoints in RCT.

Detailed comparisons will be defined in the R-SAP.

3. RSA DESIGN

This study is a multi-center, randomized, placebo-controlled trial, testing active doses of ABBV-CLS-7262 (120 mg and 240 mg), given orally once daily versus placebo. A total of approximately 300 participants will be randomized. to ABBV-CLS-7262 120 mg, ABBV-CLS-7262 240 mg, or placebo.

3.1 Scientific Rationale for RSA Design

This RSA is designed to correspond with the design of the Master Protocol and the goals of the Platform Trial.

3.2 End of Participation Definition

A participant is considered to have completed his or her participation in the placebo-controlled period of the Regimen if all planned placebo-controlled period visits, including the last visit or the last scheduled procedure shown in the Schedule of Activities (SOA), have been completed.

If a participant initiates active treatment with IP in the ATE period, he or she is considered to have completed his or her participation in the ATE period of the Regimen if all planned ATE period visits, including the last visit or the last scheduled procedure shown in the SOA, have been completed. Participants may continue to receive investigational drug in the ATE beyond Week 52, until results from the placebo-controlled period of the study are available, as applicable.

3.3 End of Regimen Definition

The end of the placebo-controlled period in a Regimen occurs when all randomized participants have completed their participation in the placebo-controlled period as defined in section 3.2.

The end of the ATE period in a Regimen occurs when all participants who have received active treatment with IP in the ATE period have completed their participation in the ATE period as defined in section 3.2.

4. RSA ENROLLMENT

4.1 Number of Study Participants

Approximately 300 participants will be randomized for this Regimen.

4.2 Inclusion and Exclusion Criteria

To be randomized to a Regimen, participants must meet the Master Protocol eligibility criteria. In addition, participants meeting all of the following inclusion and none of the exclusion criteria will be allowed to enroll in this Regimen:

4.2.1 RSA Inclusion Criteria

There are no additional RSA Inclusion Criteria from those described in the Master Protocol.

4.2.2 RSA Exclusion Criteria

- 1. Use of any moderate or strong CYP3A4 inhibitor or inducer within 10 days or 5 half-lives (whichever is longer) prior to Baseline (Table 1).
- 2. Use of any BCRP sensitive substrates with narrow therapeutic index as classified by the risk level "X" in the Lexicomp® drug interaction database (e.g., pazopanib, rimegepant, topotecan, and rosuvastatin ≥40 mg) within 10 days or 5 half-lives (whichever is longer) prior to Baseline (Table 2).
- 3. Any clinically significant ECG abnormalities, including QT interval corrected for heart rate using Fridericia's correction formula (QTcF) of > 450 msec for males or > 470 msec for females at Master Protocol Screening.
- 4. Abnormal adrenal function, defined as confirmed abnormal random cortisol ($<5 \mu g/dL$) or ACTH (>2x upper limit of normal) at Regimen Specific Screening.
 - a. Participants may undergo repeat cortisol and ACTH testing once, in order to establish normal adrenal function. If repeat cortisol and ACTH testing is abnormal, at the Investigator's discretion, the participant may undergo cosyntropin stimulation testing to establish normal adrenal function to meet eligibility criteria.

4.3 Treatment Assignment Procedures

Each participant who meets all eligibility criteria for the Regimen will be randomized to receive ABBV-CLS-7262 120 mg, ABBV-CLS-7262 240 mg, or placebo QD for approximately 24 weeks of placebo-controlled treatment and will continue on to the ATE period for approximately

52 weeks with the possibility of extending participation until the results of the placebo-controlled portion of the trial are available and a decision has been made about future clinical development.

4.4 Active Treatment Extension Eligibility

Participants who complete the 24-week placebo-controlled period will participate in the ATE unless consent is withdrawn. Participants in the 120 mg and 240 mg active treatment groups will continue to receive the same assigned dose for the ATE period. Participants in the placebo group will be assigned to active treatment with 120 mg ABBV-CLS-7262 for the ATE period. The ATE will remain blinded to dose level and original placebo-controlled treatment assignment for sites, investigators, and participants.

5. INVESTIGATIONAL PRODUCT

5.1 Investigational Product Manufacturer

IP will be provided by Calico. ABBV-CLS-7262 granules and matching placebo granules are manufactured by AbbVie, Inc. under Good Manufacturing Practice (GMP).

5.2 Labeling, Packaging, and Resupply

ABBV-CLS-7262 granules and matching placebo granules are packaged in a foil-lined sachet. Labels will be prepared in accordance with GMP and local regulatory guidelines. The labels will satisfy GMP Annex 13 requirements for labelling. All IP (i.e., sachet and kits) will be labelled with double-blind labels for the duration of the study. In the double-blind placebo-controlled period, the IP will be double-blinded to the sponsor, the regimen industry partner, sites, investigators, and participants. Unblinding for the sponsor and the regimen industry partner may occur after the database lock at the end of the double-blinded period. In the ATE period, IP will continue to be blinded to dose level and original placebo-controlled treatment assignment for sites, investigators, and participants, and each participant will be receiving active treatment with either 120 mg or 240 mg ABBV-CLS-7262.

Administration and supply of IP for each arm throughout the entire duration of the study (both the placebo-controlled period and the ATE period) will be as follows:

- ABBV-CLS-7262 120 mg: One sachet of 120 mg ABBV-CLS-7262 and one matching placebo sachet QD
- ABBV-CLS-7262 240 mg: Two sachets of 120 mg ABBV-CLS-7262 QD
- Placebo: Two placebo sachets QD

IP will be supplied by the Regimen industry partner or designated representative. No IP will be shipped to a site until a site is activated to begin enrolling participants in this Regimen.

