9.3 Regimen Specific Operating Characteristics

Clinical trial simulations customized for Regimen F (ABBV-CLS-7262) are provided in Appendix I to the R-SAP. The primary comparison of the anchor dose (120 mg) to placebo control is powered at approximately 80% to detect a 30% slowing in disease progression (common to mortality and function decline). The type I error of the regimen is 2.5% assuming no systematic differences in rates of progression across regimens contributing to the concurrent controls. More details are provided in Appendix I to the R-SAP.

[figure not shown]
Given the sample size of 165 participants on 120 mg (RCT treatment)/120 mg (ATE treatment) and 75 participants on placebo (RCT treatment)/120 mg (ATE treatment), the study will also have approximately 85% power on the CAFS at ATE Week 52, and approximately 80% power for survival through to the end of the ATE period. Such calculations were performed with assumptions for an 18-month survival rate of 70% for placebo RCT/120 mg ATE group and an 86% survival rate for 120 mg RCT /120 mg ATE group at ATE Week 52, with a 12-month accrual period (totaling a maximum study duration of 30 months) and 13% drop-out rate due to non-mortality reasons. The treatment difference for change from baseline in ALSFRS-R total score was assumed 20% slowing of disease progression rate versus delayed initiation of ABBV-CLS-7262 with a standard deviation of 9.0 at ATE Week 52 (accounting for a partial cross-over effect). An exponential distribution was assumed for power assessment of CAFS and survival endpoints. These tests for power analysis were done with a two-sided significance level of 0.05.

[figure not shown]

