This Regimen-specific Statistical Analysis Plan (R-SAP) for the Calico ABBV-CLS-7262 regimen (RGF), including the "ALS Master Protocol Regimen F (ABBV-CLS-7262) Primary Analysis, Design & Simulation Report" (RGF PADSR) as Appendix 1, specifies any modification from the default outcome measures, analysis samples, and planned analyses for the placebo-controlled period of the HEALEY ALS Platform Trial as specified in the Master SAP (M-SAP). The M-SAP and this R-SAP supplement the Master Protocol, the "ALS Master Protocol Recommended Statistical Analysis, Design and Simulation Report" (MPRDR, Appendix 1 of the M-SAP), and the RGF Regimen-specific Appendix (RSA). Please refer to the Master Protocol and the RGF RSA for details on the rationale for the study design, eligibility criteria, conduct of the trial, clinical assessments and schedule of assessments, definitions and reporting of adverse events, data management conventions, and regulatory oversight and compliance procedures. The MPRDR, any regimen-specific deviations described in the RGF RSA, and this R-SAP, including Appendix 1, are authoritative in defining the primary and interim analyses. In case of discrepancies between the RGF RSA and this R-SAP concerning use of shared placebos, this R-SAP is authoritative. In case of discrepancies between either SAP and the Master Protocol and the RGF RSA concerning matters of analysis other than the primary and interim analyses and use of shared placebos, the M-SAP and this R-SAP are authoritative. In case of discrepancies between the M-SAP and this R-SAP, this R-SAP is authoritative. In case of discrepancies between the MPRDR and RGF PADSR (Appendix 1 of this R-SAP) concerning the primary and interim analyses, the RGF PADSR is authoritative. On all matters not related to analysis, the Master Protocol and the RGF RSA are authoritative. The following table describes relationships among the relevant documents in adjudicating possible discrepancies with higher numbers indicating greater authority.

Issues potentially requiring adjudication	Master Protocol	RGF RSA	MPRDR	M-SAP	RGF R-SAP
Use of shared placebos	1	4	2	3	5
Primary and interim analysis specifications not related to use of shared placebo	1	4	3	2	.5
Statistical analysis specifications not related to use of shared placebo or primary and interim analyses	1	3	2	4	.5
All matters not related to statistical analysis	4	5	1	2	3

2. Study Design

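### Protocol 5.2 applies its supply list to both periods and gives the placebo arm only placebo sachets, which contradicts 4.4, 2.3, 9.3 and the preceding paragraph of 5.2 on what that arm receives in the ATE

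*Protocol*

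**What the plan says.** Section 5.2 of the Protocol (Regimen-Specific Appendix F, version 3.0) lists what is supplied under each assignment. The lead-in sets the scope as "Administration and supply of IP for each arm throughout the entire duration of the study (both the placebo-controlled period and the ATE period"). Three entries follow: one active and one placebo sachet for the 120 mg arm, two active sachets for the 240 mg arm, and for the third arm "Placebo: Two placebo sachets QD". No entry covers participants who move from placebo to active drug.

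Four other places in the same document describe the ATE differently for the placebo arm:

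- **Section 5.2, paragraph before the list:** in the ATE "each participant will be receiving active treatment with either 120 mg or 240 mg ABBV-CLS-7262".
- **Section 4.4:** "Participants in the placebo group will be assigned to active treatment with 120 mg ABBV-CLS-7262 for the ATE period".
- **Section 2.3:** the primary ATE comparison sets the arm on 120 mg in both periods against "placebo RCT/ABBV-CLS-7262 120 mg ATE based on combined RCT and ATE data sets".
- **Section 9.3:** the ATE power statement is based on 165 participants on 120 mg throughout and "75 participants on placebo (RCT treatment)/120 mg (ATE treatment").

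The SAP's section on governing documents says: "On all matters not related to analysis, the Master Protocol and the RGF RSA are authoritative".

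**The concern.** The list in 5.2 is an operative instruction on administration and supply, not background text. Its stated scope names both periods, so on its face it keeps the placebo arm on placebo after Week 24.

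The ATE analysis is a delayed-start comparison: early start of 120 mg against start at Week 24. Section 9.3 claims approximately 85% power on CAFS at ATE Week 52 and approximately 80% power for survival to the end of the ATE. Both figures assume that the placebo arm crosses to active drug. If that arm stayed on placebo, the comparison would be continued active against continued placebo, which is neither the contrast in 2.3 nor the one powered in 9.3. The participants concerned would also not receive what 4.4 assigns them.

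Such an error would be hard to see at site level. Sections 4.4 and 5.2 keep sites, investigators and participants blinded to dose level and original assignment in the ATE. Section 8.1 places PK sampling in the placebo-controlled period, 5.7 limits concentration-based compliance to that period, and the ATE visit lists in 6.11 contain no PK sample.

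**Working it through.** This is a comparison of texts; there is no power or error-rate figure to reproduce.

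**Step 1. Read each entry of the 5.2 list, under its stated two-period scope, against 4.4.**

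| Randomized arm | 5.2 list, applied to the ATE | 4.4, for the ATE | Agree? |
|---|---|---|---|
| 120 mg | one active and one placebo sachet | same assigned dose continues | yes |
| 240 mg | two active sachets | same assigned dose continues | yes |
| Placebo | two placebo sachets | active treatment, 120 mg | **no** |

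The two-period scope works for the first two entries and fails only for the third. That pattern is what one would expect from a lead-in written with the active arms in mind.

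**Step 2. Look for a rule that settles the conflict.**

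- The SAP's order of authority makes the Master Protocol and the RSA govern non-analysis matters and ranks the RSA highest. All the conflicting passages are in the RSA, so the hierarchy cannot choose between them.
- SAP 2.8 says kits for participants randomized to placebo hold placebo in both packet types. It names no period and describes no kit for a former placebo participant in the ATE. The SAP as a whole is written for the placebo-controlled period.
- Protocol 5.3 gives sachet composition by dose level, and 5.4 gives administration and duration. Neither adds an ATE supply rule for this arm.

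The conflict is therefore not resolved within the documents.

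**Step 3. Size, if the list were followed literally.**

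- Randomized to placebo: about 75 of about 300 (Protocol 9.1), and 75 / 300 = 25%. This is an upper bound, because 4.4 admits to the ATE those who complete the 24 weeks.
- Attrition inputs (SAP Appendix 1, section 3.1): non-mortality dropout 2% per month and mortality 5% over 24 weeks.
- 24 weeks is about 5.5 months (168 days / 30.44 days per month = 5.52).
- Expected to enter the ATE: 75 × 0.98^5.5 × (1 − 0.05) = 75 × 0.895 × 0.95 = 63.8, or about 64.

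The number actually dispensed ATE product could be somewhat lower. Section 6.10 lets participants who have stopped study drug but remain in follow-up continue into the ATE without restarting it. The planned ATE duration is approximately 52 weeks.

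**The case against.** The strongest reply is that the intent is not in doubt. One list lead-in stands against four consistent statements, one of them in the same section immediately before the list. The list can be read as sachet composition for whichever treatment a participant is taking: two sachets a day in both periods, which preserves the dose blind. On that reading the placebo entry simply lapses at Week 24. This carries weight, and it is why a drafting error is the likely explanation. It does not remove the contradiction, because the lead-in speaks of each arm and names both periods. A supply instruction should not depend on the reader overriding its stated scope.

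A reader might go further and infer any of the following, none of which the documents support:

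- **That kits were or will be assigned from this list.** Neither document says so. SAP 2.6 takes assignment from a randomization schedule and SAP 2.8 describes kit contents; neither refers to Protocol 5.2. Further dosing and dispensing detail is left to the Manual of Procedures, which is not among the documents. The link is a reason to check, not an established fact.
- **That the ATE design itself is in question.** The delayed-start design is stated consistently everywhere except in this list.
- **That participants were told one thing and would receive another.** The consent material is not available for review, so nothing can be said about it.
- **That nobody could detect an error.** Section 5.2 allows the sponsor and the regimen partner to be unblinded after the database lock of the double-blind period. That could bring a misassignment to light, although the text gives no timing relative to ATE dispensing and does not guarantee it.

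**Conclusion.** The contradiction is literal, stands in the current text, and should be corrected. It is an internal inconsistency in an operative supply rule, probably a drafting error, with no evidence of any misassigned kit.

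The size is conditional. Only if the list were followed as written would up to about 75 randomized placebo participants be affected. The estimate of about 64 rests on the SAP's simulation assumptions for dropout and mortality holding in this arm and acting independently. Neither number is an expected effect.

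In that event the damage would fall on the ATE comparison in 2.3 and on the CAFS and survival power in 9.3. The placebo-controlled primary analysis does not depend on ATE supply and is unaffected. No view is taken here on what the arm should receive; that is for the sponsor to state once and consistently.

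**What to change.** Reconcile 5.2 with 4.4, 2.3 and 9.3. Replace the single list with supply stated separately for the placebo-controlled period and for the ATE, including an explicit ATE row for participants originally randomized to placebo. Then check the kit-assignment specification for the ATE against the reconciled text and document the result; to protect the blind, someone already entitled to see assignments should do this.

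The cost is one wording change in the RSA and one check of the supply specification. No change to the sample size, the analyses or the SAP follows from it.
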